1.0 LIST OF ABBREVIATIONS

Abbreviation	Definition
AE	Adverse Event
AMRS	Addiction Medicine Recovery Services
API	Application Programming Interface
CDC	Center for Disease Control
CCTN	Center for Clinical Trials Network
CLIA	Clinical Laboratory Improvement Amendments
CoC	Certificate of Confidentiality
CFR	Code of Federal Regulations
CRF	Case Report Form
CTN	Clinical Trials Network
DM	Data Manager/Management
DSC	Data and Statistics Center
DSMB	Data and Safety Monitoring Board
eCRF	Electronic Case Report Forms
EHR	Electronic Health Record
EMA	Ecological Momentary Assessment
ERC	Ethics Review Committee
FDA	Food and Drug Administration
FWA	Federalwide Assurance
GCP	Good Clinical Practice
GPS	Global Positioning System

HEAL	Helping to End Addiction Long-term
HHS	Department of Health and Human Services
HIPAA	Health Insurance Portability and Accountability Act
HSP	Human Subjects Protection
ICH	International Council for Harmonization
IRB	Institutional Review Board
KPNC	Kaiser Permanente System in Northern California
LI	Lead Investigator
LN	Lead Node
MAR	Missing at random
MCAR	Missing completely at random
MNAR	Missing not at random
MOP	Manual of Procedures
MOUD	Medications for Opioid Use Disorder
NIDA	National Institute on Drug Abuse
NIH	National Institutes of Health
OHRP	Office for Human Research Protection
OUD	Opioid Use Disorder
PhenX	Phenotypic traits and Environmental eXposures
PI	Principal Investigator
PM	Project Manager
QA	Quality Assurance
RA	Research Assistant

RC	Research Coordinator
SAE	Serious Adverse Event
NetSCID-5	Web-based Structured Clinical Interview for DSM-5
SUD	Substance Use Disorder
UDS	Urine Drug Screen
UP	Unanticipated Problems

2.0 STUDY SYNOPSIS

Across the U.S., the prevalence of opioid use disorder (OUD) and the rates of opioid overdoses have risen precipitously in recent years. Drug overdose is being called a “modern plague” (Katz, 2017) and is now the leading cause of death of Americans under age 50, having surpassed peak death rates from gun violence, HIV, and car crashes (Centers for Disease Control and Prevention (CDC), 2018; Katz, 2017). This dramatic spike in OUD has also been accompanied by marked increases in injection-related infections (including infective endocarditis and Hepatitis C) (Centers for Disease Control and Prevention (CDC), 2016, 2017; Hartman et al., 2016; Keeshin & Feinberg, 2016), babies born with Neonatal Opioid Withdrawal Syndrome (Patrick, Davis, Lehmann, & Cooper, 2015) and healthcare and criminal justice costs (Rhyan, 2017).

Several effective medication-assisted treatments for OUDs exist. Treatment models for OUDs that include buprenorphine medication are among the most effective treatment models. Buprenorphine treatment for OUD has been shown to greatly increase opioid abstinence, reduce HIV/infectious disease risk behavior, and criminality. Greater retention in such treatment models are associated with the most positive treatment outcomes (Connock et al., 2007; Johnson, Jaffe, & Fudala, 1992; Ling et al., 1998; Sordo et al., 2017a). However, given the chronic relapsing nature of the disease of addiction, many individuals continue to engage in opioid use during treatment. Further, many individuals who enter buprenorphine treatment do not consistently take their medication or remain engaged in treatment – typically resulting in continued opioid use (which is accompanied by risk of overdose) (Fiellin et al., 2008; Schuman-Olivier, Weiss, Hoepfner, Borodovsky, & Albanese, 2014). Although many factors (e.g., stress, mental health comorbidities, and continued exposure to high risk social networks or contexts) have been shown to predict non-adherence in substance use disorder treatment (Simon et al., 2017; Weinstein et al., 2017), most studies have examined a small set of potential moderators or mediators of outcomes in treatment for OUD and may lead to over-simplified accounts of treatment non-adherence.

More frequent and longer assessment of moderators, mediators, and outcome(s) are necessary to elucidate the temporal dynamics between changes in specific mechanisms and treatment non-adherence behavior (Collins & Graham, 2002). Examining a broad array of factors impacting treatment non-adherence at multiple levels of analysis will enable a more comprehensive picture and will increase our ability to develop more impactful interventions for OUD.

Advances in **digital technologies and data analytics** have created new opportunities to assess and modify health behavior and thus accelerate the ability of science to understand and contribute to improved health behavior and health outcomes. Given the ubiquity of access to digital technologies worldwide, digital tools allow for the examination of health behavior and clinical trajectories within-individuals through intensive collection of individual-level, real-time data collected via surveys on mobile device (referred to as Ecological Momentary Assessment [EMA]), wearable sensors (on smartphones and/or smartwatches), and mapping digital footprints. Digitally-derived data allow for the development of dynamic models of health behavior to understand behavior in real-time and in response to changing environmental, social, physiological, and intrapersonal factors (Naslund et al., 2017; Spruijt-Metz, 2014). As applied to persons with OUD, digital data that offers ongoing assessment of behavior as individuals live their daily lives can help us better understand the trajectory of clinically important behaviors (e.g., treatment retention; medication adherence over time) and identify fluctuating contextual factors that greatly influence such behaviors, (e.g., patterns leading to relapse or treatment dropout).

Parent Study

This study is an ancillary study to CTN 0084 “Establishing an Opioid Registry Across Diverse Health Systems” (PI: [name]). An aim of CTN 0084 focuses on the use of EHR data from several health systems to examine the relationship between different lengths of buprenorphine retention and mortality. The optimal duration of buprenorphine treatment to reduce the risk of relapse, overdose, and mortality outcomes is unknown, although generally a longer length of treatment is related to better opioid use outcomes and lower risk of mortality (Dupouy et al., 2017; Sordo et al., 2017b; Weiss & Rao, 2017). However, retention in treatment remains a well-documented challenge and factors such as relapse, other substance use, inability to adhere to program stipulations, loss of insurance, cost, patient preference, provider practice, or health system policies can be related to discontinuation. CTN 0084 examines the distribution of buprenorphine retention, associated patient and health system characteristics, and rates of mortality, providing a high level view of this problem. This ancillary study complements the parent study by offering a “deep dive” into key factors associated with treatment retention (examining EHR data complemented by digitally-derived data) through data collected in real-time from a subset of patients in buprenorphine treatment for OUD as they live their daily lives. This ancillary study is a pilot, observational study and is not powered to test specific hypotheses.

2.1 Study Objectives

The primary objective of this study is to evaluate the feasibility of utilizing digital health technology (EMA and digital sensing) continuously over a 12-week period and collecting social media data.

The secondary objective is to examine the utility of EMA, digital sensing, and social media data (separately and compared to one another) in predicting OUD treatment retention, buprenorphine medication adherence (as captured in EHR, medical claims, and EMA data).

2.2 Study Design and Outcomes (full description in Section 14.0)

Individuals who are active in medication treatment for opioid use disorder (MOUD) with buprenorphine for at least 2 weeks will be invited to participate in the study. This project will evaluate the feasibility and benefits of digital health technologies that can be embedded in clinical trials. Feasibility will be evaluated by the percentage of eligible participants who enroll and adhere to a 12 week period of assessment using passive mobile sensing devices (smartwatch and smartphone), daily randomly prompted EMAs (that assess sleep, stress, pain severity, pain interference, pain catastrophizing, craving, withdrawal, substance use risk context, mood, context, substance use, self-regulation, MOUD adherence, and impact of COVID-19), self-initiated substance use EMA, and social media data download. Participating in the social media data download portion of the study will be optional. The secondary outcomes will be treatment retention and buprenorphine adherence through EMA and EHR/medical claims data over 12 weeks (specifically, the 12 weeks of study participation as well as the 12 months prior to when the individuals start EMAs).

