2.6 Analyses (Full Description in Section 14.0)

[figure not shown]
In order to measure the feasibility of digital health technology, we will generate descriptive statistical summaries of the level of adherence of study participants to the desired protocol (e.g., EMA response rate, smartwatch and smartphone wear/carry rate). No statistical inference is planned for this assessment. Feasibility will be evaluated via the following three independent metrics: 1) the percentage of days during the 12-week active phase enrolled participants wore/carried the smartwatch and smartphone; 2) the response rate to EMA prompts during the 12-week active phase; and 3) the percentage of participants who consent to social media data download and sparsity of social media data per participant.

In digital health data (Jain, Powers, Hawkins, & Brownstein, 2015a), the spatio-temporal granularity of information about an individual is of higher resolution than that obtained through cross-sectional or traditional longitudinal studies. Therefore, we define endpoints (dependent variables) that may occur repeatedly over a 12-week observational period, and aim to use data from smartphones, wearable devices, social media and EMA to predict, explain and detect these endpoints.

Our analyses comprise three main efforts: Predicting endpoints using passively and actively collected digital health and social media data; Explaining temporal-causal relationships between factors determined to be useful for predicting endpoints; Detecting event-specific endpoints using passively collected digital health and social media data.

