5.2 Secondary Objective(s)

The secondary objective is to examine the utility of EMA, digital sensing, and social media data (separately and compared to one another) in predicting OUD treatment retention, and buprenorphine medication adherence (as captured in EHR, medical claims, and EMA data).

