6.0 STUDY DESIGN

6.1 Overview of Study Design

Individuals with OUD who are active in outpatient buprenorphine treatment for at least 2 weeks will be recruited for the study. Potentially eligible individuals will be identified through the EHR and sent an invitational letter through secure message. Subsequently, study staff will call potential participants, and individuals interested in the study will go through a verbal consent process and complete the screening assessment by phone/video. Once it is confirmed that eligibility criteria are met, the participant will provide electronic informed consent and complete the baseline assessment by phone/video. The baseline appointments will take approximately 2.0 hours to complete, which will be done in two to three visits (preferably in two visits). Participants will wear a smartwatch and carry a smartphone (a study-supplied one or their own) that will passively collect sensor data. They will be asked to actively respond to EMA prompts through a smartphone up to 3 times daily and to self-initiate EMAs daily if substance use occurred over the 12 week study. For those who consent, social media data will be downloaded by the participant directly from the social media platform to a secure server using a remote desktop at the beginning of the study and again at the end of the study. EHR and medical claims data extraction will occur at approximately 16 weeks after study completion and will collect data 12 months prior to EMA start through 12-weeks post-EMA start. A follow-up assessment (taking approximately 45 minutes to complete assessments plus 15 minutes to instruct participants on how to return study equipment) will occur approximately 12 weeks post-EMA start by phone/video.

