7.2 Secondary Outcome Measure(s)

The secondary outcome measures will include:

1. OUD treatment retention (days retained in OUD treatment program) based on EHR data;
2. Days covered on MOUD based on EHR and EMA data; and
3. Non-prescribed opioid use (including illicit opioid use) based on EMA data.

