7.3 Other Outcome Measures

Other outcomes will include:

1. Frequency of missed buprenorphine doses based on EMA data;
2. Percentage of days with access to prescription medication exceeding a threshold (e.g., 80%) over the 12-week study period (a dichotomous variable based on pharmacy dispensation and medication orders from the EHR data extraction);
3. Number of days of non-prescribed opioid use (including illicit opioid use) in the last 4 weeks (weeks 9-12 post study consent) based on EMA data; and
4. Each non-prescribed opioid use event during the 12-week study period based on EMA data.
5. Each missed dose event during the 12-week study period based on EMA data.
6. Each missed visit to OUD treatment program during the 12-week study period based on EHR data.

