14.5 Types of Analyses

We are interested in measuring and predicting outcomes that may occur repeatedly over a 12-week observational period (e.g., patterns of daily drug use) using digital health technology. In digital health (Jain et al., 2015a) the spatio-temporal granularity of information about an individual is of higher resolution than that obtained through cross-sectional or traditional longitudinal studies. We will therefore assess the utility of using data from smartphones, smartwatches, social media and ecological momentary assessment to predict, explain and detect these outcomes.

Predicting outcomes using passively and actively collected digital health and social media data: Our approach to prediction will include regression-based methods (e.g., logistic regression), but we will also use common machine learning approaches for binary classification (e.g., random forest, support vector machines, K-means, gradient boosting). For each of these classification techniques, we will assess the utility of the various digital data for improving prediction quality. Typical evaluation methods used to assess the prediction quality include accuracy, precision, F-score, sensitivity (recall), and specificity. The relative utility of the various data for predicting outcomes will be assessed at two levels - individual features level and aggregated feature level. Interpretability of each feature and its contribution in predicting the outcome variable will be assessed using an ensemble framework, SHAP (Lundberg & Lee, 2017). In addition, we will also assess mutual information (Kraskov, Stogbauer, & Grassberger, 2004), which is a non-parametric approach of estimating the dependency between individual features and the target outcome. In another approach, features will be aggregated based on their gross categories (e.g., Facebook, Twitter, GPS, step, sleep, mood). The relative importance of each category will be evaluated based on its performance in predicting outcome (e.g., F-score).

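### Three secondary and other outcome definitions need correcting or reconciling: the anchor of the last-4-weeks EMA count, the retention and adherence window, and the source for non-prescribed opioid use

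*Combined protocol and SAP*

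**What the plan says.** **Anchor (7.3 item 3).** This outcome is the number of days of non-prescribed opioid use, from EMA, in the last 4 weeks, defined as weeks 9-12 after consent. Section 10.2.3 places consent at the first baseline appointment. The smartwatch, and the study phone if one is needed, are mailed after that. Set-up, app installation and EMA instruction take place at a second appointment, booked once the equipment has arrived. Section 8.3 defines the active phase as the 12 weeks of EMA and sensor collection. Section 10.5 sets follow-up about 12 weeks after EMA start, and 6.1 says the EHR and claims extraction "will collect data 12 months prior to EMA start through 12-weeks post-EMA start".

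**Window (2.2).** Retention and adherence, taken from EMA and EHR/claims data, are measured "over 12 weeks (specifically, the 12 weeks of study participation as well as the 12 months prior to when the individuals start EMAs". Section 2.6 says "we define endpoints (dependent variables) that may occur repeatedly over a 12-week observational period", and 14.5 says "We are interested in measuring and predicting outcomes that may occur repeatedly over a 12-week observational period". Section 7.3 item 2 defines its EHR medication-access measure as "Percentage of days with access to prescription medication exceeding a threshold (e.g., 80%) over the 12-week study period". Section 7.2 lists "OUD treatment retention (days retained in OUD treatment program) based on EHR data" and "Days covered on MOUD based on EHR and EMA data" with no window, and 14.1.2 gives none either. Sections 2.4, 3.0, 6.1, 6.2, 11.1 and 11.6.1 mention the prior 12 months only as part of the EHR/claims extraction range.

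**Source.** Section 7.2 item 3 bases non-prescribed opioid use on EMA. Section 14.1.2 item 3 bases the same secondary outcome on EHR and EMA.

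**The concern.** A consent-anchored window applied to data that begin at EMA start counts the wrong EMA days. The shift equals each participant's own delay between consent and EMA start, so the outcome covers a different stretch of the active phase in different people and is not the last 4 weeks for any of them.

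The wording of 2.2 matters because of the secondary objective in 5.2, which is to examine "the utility of EMA, digital sensing, and social media data (separately and compared to one another) in predicting OUD treatment retention". A retention count that pooled in the year before EMA start would consist mostly of time before any EMA or study sensor reading. Those data cannot predict what has already happened. Downloaded social media may reach further back (16.5), but EMA and sensing cannot.

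Two stated sources for one outcome, with no combination rule in the supplied text, mean that two analysts could follow the protocol and derive different variables.

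**Working it through.** The plan gives no figure to reproduce here. The check is day-count arithmetic plus a comparison of sections.

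**1. Anchor.** Let L be the days from consent to EMA start. Because devices are mailed and set up after consent, L is greater than 0. The documents do not state L, so the values below are assumptions.

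- Weeks 9-12 after consent are post-consent days 57 to 84.
- On the EMA clock these are days (57 − L) to (84 − L).
- The true last 4 weeks of the EMA phase are EMA days 57 to 84. For L up to 28, the overlap is 28 − L days.

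| Assumed L (days) | EMA days counted | Overlap with EMA days 57-84 | Final EMA days missed |
|---|---|---|---|
| 0 (reference) | 57-84 | 28 of 28 | 0 |
| 7 | 50-77 | 21 of 28 | 7 |
| 14 | 43-70 | 14 of 28 | 14 |
| 21 | 36-63 | 7 of 28 | 21 |
| 28 | 29-56 | 0 of 28 | 28 |

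The window remains a full 28 days inside the EMA phase while 57 − L ≥ 1, that is, for L ≤ 56.

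**2. Window.** 12 weeks = 12 × 7 = 84 days. Taking 12 months as 365 days, the pooled reading of 2.2 gives 365 + 84 = 449 days. The share before EMA start is 365/449 = 0.813, and the share in which EMA can exist is 84/449 = 0.187. These figures describe the pooled reading only.

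Set side by side, 2.6, 7.3 item 2 and 14.5 point to 12 weeks, and six sections treat the prior year as an extraction range. Section 2.2 alone attaches the prior year to the named outcomes. Its heading refers the reader to Section 14.0 for the full description, but 14.1.2 states no window for retention or days covered. The supplied text does not say whether the prior year is meant as an outcome, a covariate or a predictor.

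**3. Source.** EHR urine toxicology will be available (9.3, 11.6.1), so both the EMA-only and the EHR-plus-EMA definitions can be carried out. For opioids other than buprenorphine, 11.6.1 limits prescription data to a patient-level yes/no flag. Non-Kaiser services appear only if they were submitted as claims (11.6.1), and non-Kaiser pharmacy fills only if a claim was paid (2.4). An outside prescription with no paid claim therefore leaves the flag at no.

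**The case against.** The strongest reply is that these are wording slips in a pilot that is not powered to test hypotheses (2.0, Parent Study), and that they touch only secondary and other outcomes. That is correct and limits how much weight the point can carry. Four stronger readings are tempting, and the documents do not support them.

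- **That the plan intends a 449-day outcome which defeats the secondary objective.** The text does not require pooling. Section 2.2 can be read as two periods examined separately, or as the extraction range carried into the outcome sentence. On either reading the 84 in-study days still serve the objective. The parent study concerns lengths of buprenorphine retention, so an interest in prior treatment time may be deliberate.
- **That the 7.3 item 3 measure is unusable.** It is a complete 28-day EMA count for any lag up to 56 days. It covers the wrong 28 days, and it is one of six other outcomes.
- **That the source for opioid use will be chosen after the data are seen.** Section 14.7 refers to an Extended Data Analytic Plan that was not supplied. It may define sources, windows and the role of the look-back.
- **That a negative prescription flag settles attribution of a positive urine result.** It does not, given the paid-claim limits in 2.4 and 11.6.1. The flag also excludes buprenorphine.

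What remains is that Sections 2.2, 7.2, 7.3 and 14.1.2 conflict with one another or with the visit sequence, whatever a separate plan says.

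**Conclusion.** The point holds as a request to correct one anchor and reconcile two definitions. The anchor in 7.3 item 3 is wrong as written: the window must end before the EMA phase does, by a lag that varies between participants. The direction is certain because devices are mailed and set up after consent. The size depends on the assumed lag, with 7, 14 or 21 final EMA days missed at lags of 7, 14 or 21 days.

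The 2.2 window is internally inconsistent. The 12-week reading is the likely intent, and the 81% figure applies only if the periods were pooled. The conflict over source between 7.2 and 14.1.2 is direct; no numeric size is attached to it.

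The primary feasibility outcomes are not affected. The conclusion rests on the supplied text, without sight of the Extended Data Analytic Plan.

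**What to change.** 1. **7.3 item 3:** replace the consent anchor with weeks 9-12 post EMA start (EMA days 57-84), matching the follow-up and extraction anchors.
2. **2.2, 7.2 and 14.1.2:** state that retention and days covered are measured over the 12 weeks from EMA start, consistent with 7.3 item 2 and 14.5. Describe the prior 12 months separately as look-back and state its role, for example as a baseline covariate or predictor. If the sponsor does want prior time as an outcome, report it separately and do not pool it with the in-study period.
3. **7.2 item 3 and 14.1.2 item 3:** name the same source or sources before analysis. If EHR toxicology is included, state how it is combined with EMA, recognising that the EHR opioid-prescription flag misses prescriptions with no paid claim.
4. Check that the Extended Data Analytic Plan agrees with the corrected text.

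The cost is wording edits in four sections and two decisions before analysis: the role of the prior 12 months, and whether and how EHR toxicology is combined with EMA. No new data are needed.
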